14 REFERENCES10

1 Background and introduction

Total hip arthroplasty (THA) is an effective treatment for many hip joint diseases, able to improve patients' functional level and quality of life and to make the return to the activities of daily living possible [1] [2]. The improvement in surgical techniques had made the bilateral THA surgery possible, through one-stage procedure [3]. It seems not to be linked to increased in mortality rate or postoperative complications respect to the same two-stage procedure. [4] [5] [6].

The goal of the surgery is not only the pain relief, but also the functional recovery, which could take place through adaptive mechanisms of the non-afflicted limb. Simultaneous bilateral THA surgery doesn't allow these adaptive mechanisms and our clinical observation suggests that in this condition, the recovery of the operated limb could be faster. This is not a new hypothesis, in fact the use of the residual motor potential when adaptive strategies are not possible, has been largely demonstrated in the functional recovery of stroke patients [7]. In this case, the application of movement restrictions to the non-affected body segments and the intensive use of the affected side, promotes the motor and functional recovery [8]. Some authors suggest to apply similar approaches in other pathological conditions [9] [10].

2 Rationale of the study

Actually there are no studies investigating the motor and functional recovery of unilateral THA patients compared to simultaneous bilateral THA patients. Our clinical observation induce to speculate that simultaneous THA patients could achieve better functional and motor recovery of affected limbs caused by the impossibility to develop adaptive mechanisms with the contralateral side.

3 Object of the study

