3.2 End-points

3.2.1 Primary endpoints

The primary endpoint the evaluation of postural stability and the weight distribution during a stabilometric task performed in "open eyes" and "closed eyes" conditions, and during a "voluntary swing" condition. The postural stability and weight distribution will be evaluated through two force platforms (P-6000 BTS SpA). The platforms will calculate the weight distribution between the two lower limbs and the antero-posterior and mid-lateral displacement of the Centre of Pressure (CoP) applied on the ground. An optoelectronic system with passive markers composed of six infrared cameras (Smart DX, BTS SpA) and 4-channel surface electromyography (FREEEEMG 1000, BTS SpA) will also be used. The markers will be placed on anatomic bony landmark according to the Davis model in order to reconstruct the pelvis, hip, knee and ankle kinematic on the sagittal plane during the stabilometric task [11]. The surface electromyography will be placed on the anterior tibialis and gastrocnemius medialis of both limbs, according to SENIAM recommendation in order to evaluate the muscles activations normalized respect to the maximum voluntary contraction (MVC), the timing of muscle activation respect to the movements of the tibiotarsic joint during the "voluntary swing" and the frequency of activation during the three trials [12].

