5.1 General Design

Unilateral THA and simultaneous bilateral THA patients will be recruited. They will be evaluated through three stabilometric tests, gait analysis, two strength tests, TUG and pain (NRS). The session trials will be done the day before surgery, seven and forty day after surgery. The stabilometric tasks, the two strength tests and the NRS will be performed also after three days. The stabilometric test will be characterized by "open eyes", "closed eyes" and "oscillations" conditions. The first two stabilometric tests ("open eyes" and "closed eyes") will last 45 seconds and will be repeated three times. Patients will be asked to keep the erected station with the parallel feet placed at an intermalleolar distance of 5 cm. Their arms should be relaxed along their sides. The patient has to maintain the balance looking at a point in front of him placed at 2 meters of distance in "open

eyes" condition. During the "oscillation" task, the subject, will be asked to perform three oscillations on the platforms, one after 10 seconds from each other. The gait analysis will consist of 4 trials in which the subject will be asked to walk on the gaitwalk. During the evaluation session all subjects will wear their underwear and the performance will be recorded through two cameras (eVixta, BTS SpA) in order to check the correct performance. Before the stabilometric tests and gait analysis, the two strength tests will be performed. In the first case patients will be asked to lie in supine position, to keep the hip with the knee completely extended up to 45 ° for 10 seconds. In the second case patients will be asked to lie on his side, to keep the hip abduction with extended knee for 10 seconds. Strength tests will be repeated for the two lower limbs both. The TUG before gait analysis, will consist of standing up from a chair, walking for 3 meters, to turning a cone and to sitting again, the operator will assess the time of the test. The TUG will be repeated for three times after a break of 1 minute and only the best performance will be considered. At the end of each single test the subject will be asked to quantify pain perceived through the NRS scale. This instrument consists of a visual 10 cm line, numbered from 0 to 10, where 0 corresponds to "no pain" and 10 to "maximum pain imaginable". All the tests listed will be performed by a single operator.

6 Statistical consideration

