6.2 Analysis

The statistical analysis will be performed at the end of the study through SPSS 20.0. Categorical variables will be described in terms of proportion, while the continuous variables will be described in terms of mean and standard deviation or median and interquartile ranges. Outcomes measures will be checked for normality through Kolmogorov-Smirnov test. T-Student test will be used to confirm the homogeneity of the demographic and continuous variables before surgery for stabilometric task (weight distribution between the two lower limbs, mid-lateral and anterior-posterior displacement of the CoP, pelvis, hip, knee and ankle kinematic, muscular activation normalized by MVC, timing of the muscle activation respect to the movements of the tibiotarsic joint and activation frequency) , during gait analysis (ground reaction force, spatio temporal parameters, pelvis, hip, knee, ankle kinematic and timing of muscles activation), during the segmental strength test (time of the support of the lower limbs in the position decided by the operator), related to the TUG (execution time of the trial) and to the NRS scale (value from 0 to 10). The inter-group and intra-group differences after will be evaluated by ANOVA test for repeated measurements and then an eventual post hoc analysis will be conducted. The statistical significance value will be set at $\alpha=0.05$.

7 Withdrawal of subjects

The patients that for any reason will decide to, they will be immediately excluded from it. The incompleting acquisitions will be excluded from the analysis.

8 Forms and procedures for collecting data and data managing

An Excel file (Attachment B) will be filled in with demographic variables and outcome measures. It will be secured by a password. Only two investigators will collect the data in order to reduce errors.

9 Ethical consideration

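### Excluding every incomplete acquisition, whatever the cause, can bias the day 3 and day 7 group comparison in either direction

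*Protocol*

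**What the plan says.** Protocol section 7 has two sentences on lost data. The first concerns people who leave: "The patients that for any reason will decide to, they will be immediately excluded from it". The second concerns recordings: "The incompleting acquisitions will be excluded from the analysis". Incomplete is not defined, no reason has to be recorded, and no score is given for inability. The SAP repeats the analysis text of protocol section 6.2 and does not mention missing data.

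Section 5.1 sets the visits: "The session trials will be done the day before surgery, seven and forty day after surgery", and "The stabilometric tasks, the two strength tests and the NRS will be performed also after three days". So stabilometry, strength and pain are measured from day 3, while gait analysis and TUG start, after surgery, at day 7. The eyes-open and eyes-closed stabilometric tests each "will last 45 seconds and will be repeated three times", and an oscillation task is added. Section 3.2.1 makes this the primary endpoint: the "evaluation of postural stability and the weight distribution during a stabilometric task". Section 2 gives the expected direction: "simultaneous THA patients could achieve better functional and motor recovery of affected limbs".

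**The concern.** A patient who cannot stay standing, or cannot finish a walk, because of pain, weakness or imbalance produces an incomplete acquisition. Section 7 treats it exactly like a camera or platform fault. The technical loss is probably unrelated to recovery; the inability probably is related. A value that is missing because it would have been poor is not recovered by using the patient's other visits or by a mixed model alone.

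The groups differ in something that may well drive inability: one operated hip or two. If failure differs by group, the early comparison is between differently selected subsets. The visits exposed are those closest to surgery, where a difference in speed of recovery would be looked for.

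**Working it through.** There is no plan figure to reproduce. The documents give 30 per group and alpha 0.05, but no effect size, SD, power or failure rate. Everything below other than the 30 and the 0.05 is an assumption.

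**Model.** Latent ability is normal with SD 1, higher is better, unilateral mean 0 and bilateral mean d. A share f of each group, the lowest in ability, fails and is excluded. The measured outcome has correlation r with ability. Write λ = φ(z)/(1 − f), with z the normal quantile of f. The completers' mean is the true mean plus r·λ, so

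observed difference = d + r·(λ_bilateral − λ_unilateral).

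The bias is proportional to r, and is zero when r = 0.

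**Common ability threshold, bilateral truly worse.** Example with 10% unilateral failure and d = −0.50:
- The threshold is −1.282, so bilateral z = −0.782 and bilateral failure is 22%.
- λ_unilateral = 0.1755/0.90 = 0.195; λ_bilateral = 0.294/0.783 = 0.376.
- At r = 1: −0.50 + 0.376 − 0.195 = −0.32, which is 36% too small.
- At r = 0.6: −0.50 + 0.6 × 0.181 = −0.39, which is 22% too small.

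The ends of the range for 5-20% unilateral failure and 0.3-0.8 SD are:

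| Unilateral failure | True difference | λ unilateral, bilateral | Understated, r = 1 | r = 0.6 |
|---|---|---|---|---|
| 5% | 0.3 SD | 0.109, 0.177 | 0.069/0.3 = 23% | 14% |
| 20% | 0.8 SD | 0.350, 0.772 | 0.422/0.8 = 53% | 32% |

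**Common threshold, bilateral truly better (the study's hypothesis).** With d = +0.50, unilateral patients fail more often. At 10% and 20% unilateral failure (bilateral 4% and 9%) the observed difference is 0.39 and 0.33 at r = 1, or 0.43 and 0.40 at r = 0.6. Again it shrinks, now against the hypothesis.

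**Failure shares set separately** (positive = bilateral better):

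| Failure, unilateral / bilateral | True d | Observed, r = 1 | r = 0.6 |
|---|---|---|---|
| 20% / 20% | +0.50 | +0.50 | +0.50 |
| 10% / 30% | +0.50 | +0.80 | +0.68 |
| 10% / 30% | 0 | +0.30 | +0.18 |
| 10% / 30% | −0.50 | −0.20 | −0.32 |

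For the third row, λ is 0.1755/0.90 = 0.195 and 0.348/0.70 = 0.497, a gap of 0.302. With 27 and 21 completers, a single-visit comparison by normal approximation gives:
- r = 1: completer variances 0.712 and 0.493; SE = √(0.712/27 + 0.493/21) = 0.223; 0.302/0.223 = 1.35; false-positive rate about 27% against a nominal 5%.
- r = 0.6: about 10%.

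**The case against.** A reader might infer that the rule removes the worst recoverers and so shrinks the early difference. The documents do not support that direction. Shrinkage follows from one ability threshold common to both groups, which nothing in the plan establishes. With unequal failure the difference can grow or appear from nothing, and with equal shares it does not move. Nor can one say that the rule favours the study's hypothesis; that requires bilateral patients to fail more often, and no failure rate is given for either group.

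A reader might also take every incomplete acquisition to mean poor recovery. That is too absolute. The sentence may cover technical losses. It excludes acquisitions, not patients: the two quiet-standing tests are done three times, there are four gait trials, and TUG keeps the best of three, so one failed repeat need not lose the patient. Strength is scored as the "time of the support of the lower limbs in the position decided by the operator", so a short hold can be a valid value.

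Failure may also be rare. Patients are aged 40 to 65 and must be able to walk 50 m unaided. At 2% unilateral failure and correlation 0.6, the common-threshold understatement over 0.3-0.8 SD is only 8-12%. These points limit the size and leave the direction open. They do not remove the problem: the rule applies whatever the cause, and nothing recorded under it would show afterwards which case had occurred.

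Finally, worst rank does not suit every outcome. Weight distribution, kinematics, EMG timing and voluntary oscillation have no stated worse direction. A rank test also has no baseline term, in a non-randomised comparison. That objection stands, and it limits the remedy.

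**Conclusion.** The concern holds as a risk of bias of unknown sign. Section 7 is a stated rule, and following it deletes outcome-related failures together with technical ones at days 3 and 7. The direction and size cannot be derived from the documents.

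Under a common threshold, 5-20% unilateral failure and bilateral patients 0.3-0.8 SD worse, the understatement runs from 23-53% (perfect correlation) through about 14-32% (correlation 0.6) to zero (no correlation). With no true difference and 10% versus 30% failure, completers differ falsely by about 0.30 SD in favour of the bilateral group at perfect correlation, and 0.18 SD at 0.6. The false-positive rates in the working are for one visit and do not measure error in the planned repeated-measures ANOVA. The plan should be changed, but the figures show what could happen and do not predict what will.

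**What to change.** Replace the sentence in section 7, and carry the same rules into the SAP:

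- **(a)** A recording lost to a technical fault is missing.
- **(b)** A task the patient could not do or finish is coded 'unable' in the existing Excel file, at the visit. Valid repeats and short strength holds are kept as values.
- **(c)** The proportion unable is reported and compared by group, visit and task.
- **(d)** For outcomes whose worse direction is declared in advance, for example quiet-standing CoP displacement (days 3 and 7) and TUG time (day 7), a pre-specified rank comparison gives 'unable' the worst rank. It is reported beside the planned repeated-measures ANOVA, whose early-visit results are described as applying to patients able to complete the task.

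The cost is one extra code, a few SAP lines and a few extra analyses, with no added test or patient. The rank comparison gives no mean difference in millimetres or seconds.

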9.1 Patient protection

The responsible investigator will ensure that this study is conducted in agreement with the Declaration of Helsinki and with the laws and regulations of the country, whichever provides the greatest protection of the patient.

The protocol has been written, and the study will be conducted according to the ICH Guideline for Good Clinical Practice. The protocol and its annexes are subject to review and approval by the competent Independent Ethics Committee(s) (“IEC”).

9.2 Subject identification – Personal Data protection

All records identifying the subject must be kept confidential and, to the extent permitted by the applicable laws and/or regulations, not be made publicly available. The name of the patient will not be asked for nor recorded at the Data Center. A sequential identification number will be automatically attributed to each patient registered in the study. This number will identify the patient and must be included on all case report forms. In order to avoid identification errors date of birth, sex, weight height will also be reported on the case report forms. Only people who are actively involved in the study can access to the database. Each subject will be informed by means of an appropriate data protection module and each of them will also be sign an informed consent without which he / she will not be involved in the study.

9.3 Informed consent

All patients will be informed of the aims and the development of the study. They will be informed as to the strict confidentiality of their patient data. It will be emphasized that the participation is voluntary and that the patient is allowed to refuse further participation in the protocol whenever he/she wants. Documented informed consent must be obtained for all patients included in the study before they are registered at the Data.

10 Conflict of interest

No one between members study has a conflict of interest.

11 Data ownership

According to the ICH Guidelines on Good Clinical Practice and considering the study as a single-institution one the owner of the data is Humanitas Research Hospital.

12 Publication Policy

After completion of the study, the project coordinator will prepare a draft manuscript containing final results of the study on the basis of the statistical analysis. The manuscript will be sent to an appropriate scientific journal. All publications, abstracts, presentations, manuscripts and slides including data from the present study will be reviewed by the Study Coordinator.

13 Study time table

1. Patients enrollement : January 2018

2. Data analysis: May 2018
3. Submission of the report: July 2018

14 References

1. Ganz S. A historic look at functional outcome following total hip and knee arthroplasty. *Top Geriatr Rehabil.* 2004; 20; (4): 236-252.
2. Learmonth ID1, Young C, Rorabeck C. The operation of the century: total hip replacement. *Lancet.* 2007; 27; 370 (9597): 1508-19.
3. Alfaro-Adrián J1, Bayona F, Rech JA, Murray DW. One- or two-stage bilateral total hip replacement. *J Arthroplasty.* 1999; 14(4): 439-45.

OFFICIAL TITLE: Functional recovery after monolateral or bilateral total hip arthroplasty

PROTOCOL IDENTIFYING NUMBER: CLF17/02

DATE: 14/12/2017

Statistical analysis plan

The statistical analysis will be performed at the end of the study through SPSS 20.0. Categorical variables will be described in terms of proportion, while the continuous variables will be described in terms of mean and standard deviation or median and interquartile ranges. Outcomes measures will be checked for normality through Kolmogorov-Smirnov test. T-Student test will be used to confirm the homogeneity of the demographic and continuous variables before surgery for stabilometric task (weight distribution between the two lower limbs, mid-lateral and anterior-posterior displacement of the CoP, pelvis, hip, knee and ankle kinematic, muscular activation normalized by MVC, timing of the muscle activation respect to the movements of the tibiotarsic joint and activation frequency) , during gait analysis (ground reaction force, spatio temporal parameters, pelvis, hip, knee, ankle kinematic and timing of muscles activation), during the segmental strength test (time of the support of the lower limbs in the position decided by the operator), related to the TUG (execution time of the trial) and to the NRS scale (value from 0 to 10).

The inter-group and intra-group differences after will be evaluated by ANOVA test for repeated measurements and then an eventual post hoc analysis will be conducted. The statistical significance value will be set at $\text{Alpha}=0.05$.
